1. SYNOPSIS

Study Title	Sore throat secondary to endotracheal intubation: the role of neutrophil activation
Objective	The study is aimed at identifying neutrophil surface changes that occur during tracheal injury secondary to endotracheal intubation and to correlate them with the development of sore throat.
Study Period	Planned enrollment duration: 1 year Planned study duration: Subjects will participate from time of consent prior to surgery through approximately 120 minutes following extubation.
Number of Patients	60 evaluable patients and 25 evaluable healthy controls
Study Treatment	Patients will undergo placement of an endotracheal tube (ETT) as standard of care. Tracheal lavage will be conducted using 5 mL of sterile saline solution by a push/suction technique. Specimen samples obtained by wall suction will be collected at 2 time points following intubation. Blood samples will be obtained at 2 time points, simultaneous with the collection of the tracheal specimens. Healthy volunteers will have a blood draw.
Study Design	This study is prospective.
Inclusion and Exclusion Criteria	Inclusion: 1. Ages 18 to 65 2. American Society of Anesthesiologists Physical Status Classification (ASA) I and II as determined by the study physician as this is a subjective measure. 3. Required to have endotracheal intubation 4. Scheduled for short admission (<23 hrs), or ambulatory orthopedic surgery (ankle, shoulder, or extremity surgery); general surgery (exploratory laparotomy, cholecystectomy, ventral or inguinal hernia repair); obstetric/gynecological surgery (total abdominal hysterectomy, bilateral salpingo-oophorectomy); urologic surgery (nephrectomy, prostatectomy), lumbar spine surgery (discectomy, one or two level lumbar fusion) procedures

CONFIDENTIAL: This document is the intellectual property of [name]. Acceptance of this document constitutes the agreement by the recipient that no unpublished information contained herein will be published or disclosed without prior written approval.

DoCTR

	
5. Provide informed consent.
 
Exclusion:
 
 1. Active pulmonary disease within 5 days prior to enrollment 2. On immunosuppressive medications 3. Previous tracheal surgery 4. On azithromycin 5. Diabetes 6. Pregnancy 7. Smoking history of less than 6 weeks prior to surgery 8. Surgery or intubation within 5 days of surgery 9. Planned surgical procedure involving neck or thoracic regions 10. Active pulmonary disease 11. Autoimmune disease (HIV, AIDS, Rheumatoid Arthritis) 12. Hepatitis B or C, or active Hepatitis A 13. Cancer 
Healthy Controls: Inclusion:
 
 1. Ages 18 to 65 2. Provide informed consent.
Measurements	
Lavage Processing
 
Tracheal lavage fluid specimens will be placed on ice and transported immediately to our laboratory. A sample of 0.25cc or less will be removed for cell count and differential count. We will do total cell counts using tryptan blue to check viability of cells. Remaining whole fluid will be centrifuged at 1500 rpm for 15 minutes at 4° C and supernatants frozen in aliquots.
 
Neutrophil assessment and purification
 
Neutrophils will be counted in the tracheal lavage and peripheral blood with a HEMAVET analyzer (Drew Scientific). Neutrophils will be purified by immunomagnetic bead-mediated negative selection with biotin-labeled antibodies (e-biosciences) specific for CD11b, CD11c, CD14, CD16 CD62L, CD54, CD32, CD88, and CD66b. Flow cytometry will be used for assessment of neutrophil surface receptor presence.
 
Reactive Oxygen Species (ROS) determination
 
Neutrophil production of ROS will be assessed with the fluoro-probe dihydrorhodamine.
 
Interleukin Assays
 
Accumulation of interleukin 1 (IL-1), IL-4, IL-6, IL-8, IL-10, IL-12, IL-17, IL-23p19, (transformin growth factor 1 (TGF β-1) and tumor necrosis factor alpha (TNF-α) in culture will follow stimulation with formylated peptides by immunosorbent assay (ELISA) for human

CONFIDENTIAL: This document is the intellectual property of [name]. Acceptance of this document constitutes the agreement by the recipient that no unpublished information contained herein will be published or disclosed without prior written approval.

DoCTR

	
cytokines (R&D Systems, Minneapolis, MN).
 
Toll-like Receptors (TLR) Determination of TLR-2, TLR-4 and TLR-9 and Mitochondrial DNA will be done by PCR.
 
Neutrophil extracellular traps (NETs) formation Neutrophil cells will be stained and photographic documentation of the NET presence will be documented.

Statistical Methodology
	
The primary aim of this study is to describe the inflammatory changes that result in a neutrophil surface receptor expression unique to the interaction between the trachea and ETT resulting in sore throat. Blood samples will be obtained and neutrophil cells (PMN) will be isolated for analysis at the same time intervals as the tracheal lavage samples. Individual indicators of inflammation (PMN, cytokines, clusters of differentiation –CD, TLR's as described above) will be compared to baseline values of these variables measured at time zero. We will compare neutrophil (PMN) changes between patients who developed sore throat and those who do not by using the Wilcoxon rank sum test, since we expect the data to be non-normally distributed. With a sample size of 60 patients, we will have at least 80% power to detect large differences (Cohen's $D \geq 0.8$) between the sore throat and non-sore throat groups with an alpha level of 0.05 and assuming that half of the participants report a sore throat following intubation. As our pilot study is exploratory, we did not inflate our sample size to account for multiple testing. We will confirm any identified associations found in our pilot study with a future larger study. Subjects who undergo intubation attempts $\times 2$ or greater will be considered a subset population and not part of the 60 evaluable patients. Assuming that lack of sore throat relates to anti-inflammation, measuring a biomarker such as IL-10, may provide information on the regulatory function of this cytokine. We have observed that IL-10 at a concentration of 200 pg/ml generated by PMNs inhibited reactive oxygen species burst from alveolar macrophages challenged by LPS. Power analysis was conducted for two tailed T-test using the following assumptions: a standard deviation of 100 pg/ml. A difference of 75 pg/ml between the two groups will be considered a significant difference. We will need approximately 30 patients per group for an alpha 0.05 and Beta of 0.2.

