Several systemic diseases and certain antibiotics may alter PMN responsiveness to injury. A variety of systemic diseases such as diabetes, rheumatoid arthritis, acute lung injury and several others may affect local PMN responses to injury by altering inflammation, apoptosis and proper anti-inflammation. In the case of diabetes with microangiopathy surface receptor CD11b was elevated and CD62L was decreased²⁷. The impact of macrolide antibiotics and in particular azithromycin in the improved outcome of respiratory diseases such as acute lung injury (ALI), community-acquired pneumonia (CAP) and ventilator associated pneumonia (VAP) appear to be mediated by its anti-inflammatory properties. In particular azithromycin may affect PMN activation, PMN survival, oxidative burst, and attenuation of nuclear factor- κB ²⁸, therefore modulating the inflammatory response. It is not known the exact effect of these systemic factors in the local expression of neutrophils at the tracheal level, therefore our interest to compare local and systemic PMN activation in the healthy subject.

CONFIDENTIAL: This document is the intellectual property of [name]. Acceptance of this document constitutes the agreement by the recipient that no unpublished information contained herein will be published or disclosed without prior written approval.

DoCTR

A variety of biomaterials activate PMN in blood. The endotracheal tubes contain a biomaterial known as di-(2-ethyl-hexyl)-phthalate or DEHP as it is commonly known. Studies in human and rat blood have shown its ability to increased CD-11b expression in PMN cells²⁹. The effects on PMN of neonates also include inhibition of chemotaxis, stimulation of oxidative metabolism, and upregulation of NADPH-oxidase-1³⁰. DEHP is the only plasticizer approved for human devices by the U.S. Food and Drug Administration. Studies of materials involved either human blood samples, or *in vitro*, or rat models, none have *in vivo* local activation of PMN cells.

Significance of intubation related sore-throat in airway inflammation VAT/VAP:

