2.3.2 Exclusion Criteria

1. Active pulmonary disease within 5 days prior to enrollment
2. On immunosuppressive medications
3. Previous tracheal surgery
4. On azithromycin
5. Diabetes
6. Pregnancy
7. Smoking history of less than 6 weeks prior to surgery
8. Surgery or intubation within 5 days of surgery
9. Planned surgical procedure involving neck or thoracic regions
10. Active pulmonary disease
11. Autoimmune disease (HIV, AIDS, Rheumatoid Arthritis)
12. Hepatitis B or C, or active Hepatitis A
13. Cancer

Healthy Controls:

Inclusion:

1. Ages 18 to 65
2. Provide informed consent

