2.4.3 Pre-Study Period

Subjects who are potential candidates for the study will be educated as to the study procedures, benefits, and potential risks. Each subject who qualifies for entry into the study on the basis of inclusion/exclusion criteria, and completion of an informed consent will be assigned the next available patient number. This indicates enrollment in the study. Subjects who drop out of the study prior to completing the study will be replaced by using the next available patient number.

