2.4.4 Study Period

Subjects will participate from intubation time to the immediate post operative period.

After the placement of the endotracheal tube (Hi-Lo™ Evac Mallinckrodt), tracheal lavages will be performed using 5 milliliters of sterile saline solution by a push/suction technique. Wall suction will be set to a minimum in order to minimize tracheal injury and to comply with standards of medical care. The same procedure for collection of tracheal sample will be repeated at the end of the surgical procedure, immediately prior to removal of the ETT. The specimen will be collected in a sterile container and placed in a laden ice container for transportation and immediate processing.

A simultaneous blood sample of approx 5cc, will be collected by venipuncture or by sampling from intravenous or arterial line if available at the end of the surgical procedure, immediately prior to removal of the ETT. A total of approx 5cc blood will be collected for research purposes.

Review of the medical record will be conducted for data acquisition of medical history, and preoperative blood test results to determine enrollment in the study according to the specified inclusion or exclusion criteria protocol. Physiologic and demographic measurements such as temperature, oxygenation, and blood pressure, gender, body mass index and coexisting diseases will be recorded as per anesthesia records. All data will be de- identified. All patients will be asked to respond to presence or absence of sore throat and its degree of intensity using a Visual Analogue Scale (VAS) sliding scale at 120 minutes post extubation and following a specific cognitive assessment performed by the recovery room nurses as part of their discharge protocol. Cognitive evaluation will include patient interview to determine the following: Orientation to time, place, person and situational (Why are you here?).

Healthy volunteers

A blood sample of approx 20cc, will be collected by venipuncture for research purposes to challenge the neutrophils with necrotic tissue obtained from laboratory cultured cells and look for markers of neutrophil activation that also will include CD35/CD49b and the previously approved CD markers

CONFIDENTIAL: This document is the intellectual property of [name]. Acceptance of this document constitutes the agreement by the recipient that no unpublished information contained herein will be published or disclosed without prior written approval.

DoCTR

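### Healthy controls are admitted on age and consent alone, so donor health is left to a label in the exploratory volunteer-versus-airway comparison (minor; cheap improvement)

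*Combined protocol and SAP*

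**What the plan says.** The synopsis plans for "60 evaluable patients and 25 evaluable healthy controls". The patient criteria include ASA class I or II and 13 exclusions, among them diabetes, azithromycin, immunosuppressive drugs, recent smoking, active pulmonary disease and autoimmune disease. After these comes a separate heading, "Healthy Controls: Inclusion", whose complete content is "1. Ages 18 to 65 2. Provide informed consent". Section 2.3.2 repeats the same two items under "Healthy Controls", after the patient exclusions.

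Section 2.4.3 refers to "Each subject who qualifies for entry into the study on the basis of inclusion/exclusion criteria", which for controls means those two items. In section 2.4.4 the medical-record review uses "preoperative blood test results to determine enrollment in the study according to the specified inclusion or exclusion criteria protocol"; this stands in the patient text, before the volunteer subheading. The volunteer paragraph then describes only the draw: "A blood sample of approx 20cc, will be collected by venipuncture for research purposes to challenge the neutrophils with necrotic tissue". Section 4.3 adds flyers and consent, and section 4.5 adds a balance of women and men.

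Section 2.1 gives a reason why donor health could matter: "A variety of systemic diseases such as diabetes, rheumatoid arthritis, acute lung injury and several others may affect local PMN responses to injury". It says the same of azithromycin. Section 2.5.10 compares the volunteer blood neutrophil changes with those in injured airway neutrophils by Student's t-test. The Healthy Volunteers text in section 2.1 says that similar changes would indicate a good human model of airway inflammation.

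**The concern.** Patients are screened for factors that the protocol believes may alter neutrophil behaviour. The volunteers whose neutrophils are set beside theirs are not. Someone taking azithromycin, or with well-controlled diabetes or rheumatoid arthritis, meets the written criteria for a control.

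At stake is how the laboratory model is read. If some donors have altered neutrophils, a difference from the airway cells could reflect donor health, or a real difference could be blurred and taken as similarity. Unless donor status is recorded, no later analysis can separate the two.

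**Working it through.** **1. The text.** The two-item list is identical in the synopsis and in 2.3.2, and in 2.3.2 it is followed directly by section 2.4, so a broken table does not explain it. Sections 2.4.3, 2.4.4, 4.3 and 4.5 add no health criterion for volunteers. Could the 13 exclusions be meant for everyone? Section 2.3 is titled for patients, controls have their own heading after the exclusions, age and consent are restated for them, and several exclusions refer to an operation that volunteers do not have. The plain reading is that they do not carry over.

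**2. What section 2.1 supports.** It names diabetes, rheumatoid arthritis, acute lung injury and azithromycin, and says that they may affect responses. Its finding on CD11b and CD62L concerns diabetes with microangiopathy. It calls the effect at tracheal level unknown and gives no size. It does not mention smoking or immunosuppressive drugs; the ground for those two is only that they exclude patients.

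**3. Can a size be derived?** No. The plan gives no effect size, SD or power for the 25 volunteers, so there is no stated figure to reproduce, and no figure for how many donors might be affected or by how much. What follows is an illustration on assumed values.

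Assumptions: levels are compared rather than changes; SD = 1; two-sided alpha 0.05; 25 volunteers against n = 60 or n = 30 airway comparators (2.5.10 gives no number); k of 25 donors shifted by s SD in the same direction; true difference 0 or 0.8 SD.

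- Bias in the volunteer mean: b = (k/25) × s.
- SE = √(1/25 + 1/n), which is 0.238 for n = 60 and 0.271 for n = 30.
- Rejection probability: noncentral t with 23 + n degrees of freedom. The noncentrality is b/SE when the true difference is 0, (0.8 − b)/SE when the shift is toward the airway value, and (0.8 + b)/SE when it is away.
- False difference means rejecting when the true difference is 0. False similarity means not rejecting when it is 0.8 SD.

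Each cell gives n = 60 / n = 30.

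| k, s | b | False difference | False similarity, shift toward airway | False similarity, shift away |
|---|---|---|---|---|
| 0 | 0 | 5.0% / 5.0% | 8.7% / 17.4% | 8.7% / 17.4% |
| 1, 0.5 | 0.02 | 5.1% / 5.1% | 10.1% / 19.3% | 7.4% / 15.6% |
| 2, 1.0 | 0.08 | 6.3% / 6.0% | 15.2% / 25.8% | 4.5% / 10.9% |
| 5, 1.0 | 0.20 | 13.2% / 11.2% | 29.8% / 41.5% | 1.4% / 4.8% |

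Simulation that includes the extra variance from mixing donors changes the last row modestly: false difference 12.2% / 9.9%, and false similarity (shift toward) 31.7% / 44.3%. One donor up and one down by 1 SD gives false similarity of 9.1% / 18.4%, close to no effect.

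**4. Levels or changes.** Section 2.5.10 speaks of changes under different laboratory conditions. If each donor's challenged cells are set against that donor's own unchallenged cells, a constant shift d cancels: (challenged + d) − (unchallenged + d) = challenged − unchallenged. The table would then not apply, and only an altered response to the challenge itself could bias the result.

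**The case against.** The strongest reply is that the word healthy carries meaning. The group is called healthy throughout, the flyers recruit healthy volunteers, and section 2.1 follows its list of diseases and drugs by stating an interest in the healthy subject. Few people with overt disease would come forward, and the flyers and consent pages are not available to check. This largely stands for overt disease. It does not settle current azithromycin use, recent smoking or well-controlled disease. For patients, the protocol did not rely on a general label: it used the ASA class and named the conditions.

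A second reply is that the error rates above depend on levels being compared, on a common direction of shift and on several affected donors, and that the plan never says a non-significant t-test counts as similarity. This stands. No passage suggests that a fifth of volunteers would be affected, and section 2.1 gives no common direction across markers and exposures.

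A reader might infer that the volunteer results are already biased toward similarity, or that the study's main result is compromised. The documents support neither. The direction is open, the changes that 2.5.10 describes may remove a constant shift, and the Wilcoxon comparison of patients with and without sore throat involves no volunteers.

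**Conclusion.** The gap in the eligibility text is real: controls qualify on age and consent, and nothing describes how health is checked. It is minor. It touches one exploratory comparison, which is not among the outcomes in 2.5.7 and 2.5.8 and which is limited in any case by setting blood against airway and in vitro against in vivo.

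The size and direction of any bias cannot be derived from the documents. On the assumptions above, one or two affected donors move the volunteer mean by 0.02 to 0.08 SD, which is small. Only several donors shifted the same way would matter on a comparison of levels, and a shift away from the airway value would lower false similarity rather than raise it. The conclusion rests on the text; the percentages only illustrate it. This is a cheap improvement, worthwhile because donor health is a source of variation that a short screen can reduce.

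**What to change.** - In the synopsis and 2.3.2, state that the non-surgical patient exclusions also apply to healthy controls, timed to the blood draw. The items tied to surgery need not carry over. The smoking item is timed to surgery and must be reworded for volunteers; its present wording is unclear for patients too.
- Check the criteria with a short questionnaire before the draw.
- Record the answers, so that the t-test comparison in 2.5.10 can be repeated without any affected donor.
- For volunteers already drawn, collect the answers only where they can be recontacted while the identifier link exists (section 3.3.3 has it destroyed at study end). Otherwise report their status as unknown.

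Cost: a brief amendment, one form and slightly slower volunteer recruitment. The patient part of the study does not change.

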2. STUDY PROTOCOL

2.1 Background and Significance

Background and preliminary Studies:

Endotracheal intubation results in a high incidence of sore throat. Placement of an endotracheal tube (ETT) is essential for the administration of general anesthesia. Approximately 60 thousand surgical cases are performed every day in the United States that require general anesthesia. The ETT has been implicated in local tracheal injury, development of postoperative sore throat (POST)^{1,2,3,4,5,6}, tracheitis and pneumonia⁷. POST is ranked high by patients along with pain and nausea as an undesirable outcome following general surgery^{1,2,3,4}. Although sore throat tends to be more evident in the first 24 hours, its presence has a negative influence on patient satisfaction post-surgery^{2,4}. The incidence of POST has been reported around 50% in several studies following general endotracheal anesthesia and appears to affect a broad range of patients^{1,2,3,4}. Some studies have shown a greater incidence of sore throat in young female patients who received succinylcholine, and underwent gynecological procedures; other studies have not shown a significant gender difference⁴. Although the exact pathophysiology of POST has not been elucidated, we recently showed that various arms of the innate immune system are activated following ETT placement^{5,6}. Notably, we observed the expression of inflammatory mediators, complement C5a activation and neutrophil infiltration in the mucosal tissues and the trachea in the absence of bacterial infection. However, we did observe mucosal surface injury. As it has been clearly shown that neutrophil infiltration and activation can be driven in response to sterile cell death⁸, our preliminary data suggest that the link between ETT placement and neutrophil accumulation is through the injury to mucosal cells.

PMN infiltration found significant in our previous studies of tracheal inflammation. In a pilot swine study⁵ we documented a reproducible pattern of inflammation in the peritracheal area in which all markers measured displayed a positive increase over a period of time (6 hours). A similar pattern was documented in our human study⁶ in which we found that despite intubating under controlled conditions by an experienced practitioner, tracheal injury was still demonstrated (Figure 1). In both studies (swine and human), we measured cellular concentration (polymorphonuclear cells) and a group of proteins (cytokines) that indicate cellular responses to injury. In both groups, a significant neutrophilic reaction was documented, hence the reason for the study.

Significance of PMN phenotype in local tracheitis induced by endotracheal intubation. If our hypothesis is correct we predict that patients with sore throat will have a different PMN pro-inflammatory activation phenotype compared to patients with no sore throat, and we anticipate that the neutrophils will have a regulatory phenotype (IL-10 expression). Determination of PMN phenotypes will be essential in future research planning as sore throat may represent a group of patients more prone to developing active airway inflammation and bacterial seeding in different segments of the lower airways. PMN activation is a desirable effect to clean up acute inflammatory products but unopposed inflammatory activity may be more detrimental to local tissue homeostasis preventing the resolution of inflammation.

CONFIDENTIAL: This document is the intellectual property of [name]. Acceptance of this document constitutes the agreement by the recipient that no unpublished information contained herein will be published or disclosed without prior written approval.

DoCTR

Endotracheal intubation relates to Ventilator-associated pneumonia. The exact etiology between tracheal injury and lower airway inflammation is quite unclear. The prevailing view is that intubation-induced inflammation is caused by bacterial pathogens introduced by the endotracheal tube. However, our previous studies have suggested little evidence of bacterial pathogens in the upper airway, with ample evidence of upper tracheal epithelial injury, neutrophil recruitment and inflammatory cytokine release during short term intubation. Thus, we hypothesize that intubation-induced inflammation is predominantly a sterile tracheal injury response that may compromise homeostatic barriers important in preventing subsequent infection. Interestingly, recent studies have suggested the existence of different neutrophil subtypes with pro- and anti-inflammatory (immunosuppressive) functions¹². Some patients may avoid the consequences of upper airway injury by recruiting neutrophil populations with immunosuppressive factors that promote tissue regeneration and the resolution of inflammation.

Importantly, several reports have suggested there is a relationship between endotracheal intubation and subsequent development of ventilator-associated pneumonia (VAP) with clear implications on overall lung function and patient morbidity. In particular, studies of ventilator-associated tracheobronchitis (VAT), indicate that 10- 32% of intubated patients diagnosed with VAT developed VAP³³. The use of non-invasive positive pressure ventilation in COPD, respiratory insufficiency, immuno-compromised and congestive heart failure patients have shown to decrease the incidence of VAP dramatically, supporting the notion that the endotracheal tube is a major culprit in respiratory inflammation and infection³⁴.

The exact pathophysiology of endotracheal tube-associated pneumonia has not been elucidated although the endotracheal tube has been viewed as a major factor in development of VAP. A variety of endotracheal tube modifications (different cuff design, antibiotic coating, and addition of suction

channels) have been designed to limit bacterial colonization and VAP have shown only small improvement in outcome for our patients³⁵ suggesting the need to better understand how endotracheal tubes promote tracheal inflammation to better prevent distal airway diseases such as VAT and VAP.

[figure not shown]
[figure not shown]

Figure 1. Polymorphonuclear cells (PMNs) as a percentage of total cells in human trachea lavages obtained from 11 subjects who responded to post-operative sore throat questionnaire. Median time to end of surgery was 3 hours.

Sore throat and PMN elevation correlated in intubated patients. We conducted a human study of tracheal intubation and asked patients to described the presence or absence of sore throat after surgery, and found that the PMN elevation (figure 1) was slightly different between symptomatic and non-symptomatic subjects, albeit the population number was

CONFIDENTIAL: This document is the intellectual property of [name]. Acceptance of this document constitutes the agreement by the recipient that no unpublished information contained herein will be published or disclosed without prior written approval.

DoCTR

small. The initial markers of inflammation detected, such as PMN and protein, increased steadily ($p<0.01$) over time (average 3.2 hours) in human subjects. Neutrophils and cytokines are important components of an organized inflammatory reaction and since several of the cytokines documented may have their origin in the PMN cells, we decided to investigate PMN activation. There are studies evaluating the airway response to injury or infection, but to our knowledge, none have been related to upper tracheal inflammation and in particular the activation of PMN cells in the development of sore throat.

Cytokines produced by PMNs participate in modulation of inflammation and anti-inflammation. Cytokines are proteins produced by a variety of cells including neutrophils⁹. We measured several cytokines (TNF- α , IL-1 β , IL-6, and IL-8) in the human tracheal specimens obtained. Our findings included a progressive elevation of all cytokines measured. TNF- α was not found initially but after the first hour it became significant ($p<0.01$). Importantly, some cytokines can delay neutrophil apoptosis, which can lead to substantial increases in mucosal inflammation¹⁰. One particular cytokine TNF- α has pro or anti-apoptotic actions in neutrophils depending on whether Nfk- β is activated, a key transcriptional regulator that inhibits cell death¹¹. Besides controlling survival, cytokines released by neutrophils can promote chemotaxis (IL-8), stimulate revascularization (VEGF), promote activation of other myeloid cells (GM-CSF, IL-6, IL-1 β) and resolve inflammation (IL-10)¹². Our observation regarding PMN derived cytokines and their participation in an inflammatory response is consistent with findings described in several studies^{9,10,11,12}.

PMN activation occurs in response to bacterial and non-bacterial stimulants. Neutrophils are mobilized from the bone marrow and travel to a site of injury or infection following specific chemoattractant gradients released by injured tissue. Several chemoattractants such as interleukin 8 (IL-8), leukotrienes, prostaglandins, complement 5a (C5a), platelet activating factor (PAF) and formylated peptides (fMLP) are known to control local neutrophil accumulation¹³. Lipopolysaccharide (LPS) is present in gram-negative bacteria and may promote the release of inflammatory cytokines such as tumor necrosis factor (TNF- α) and IL-1 β . Neutrophils can be activated not only due to bacterial infiltration but also may be activated under sterile conditions¹⁴. Danger associated molecular patterns (DAMPS) released by injured cells (e.g. mitochondrial DNA, ATP, Heat shock proteins) following ischemia-reperfusion injury, trauma or chemical injury are recognized by pattern recognition receptors (PRR) which in turn generate innate immune responses¹⁵. One well characterized class of PRRs, are Toll-like receptors (TLRs). TLR2 and TLR4, for example recognize the DAMP heat shock protein 60 while TLR9 recognizes mitochondrial DNA. Interestingly, DAMPS mimic the effects of microbial pathogen-associated molecular patterns (PAMPs)^{15,16} such as LPS and can drive neutrophilic infiltration without the presence of microbial antigens¹⁵. Sterile inflammation results when tissue injury occurs in the absence of infectious organisms and presents a clinical picture characterized by local redness, swelling, heat and pain.

Surface expression of encoded proteins is present in PMN cell during injury. Continuous exposure to an antigen will result in neutrophil surface expression –*Clusters of Differentiation* (CD)-, mediated by β 2-integrins which are expressed only in neutrophil cells¹⁷. Cellular adhesion to plasma proteins such as intracellular adhesion molecule-1 (ICAM-1)¹⁸ (CD54) is mediated by integrins in

CONFIDENTIAL: This document is the intellectual property of [name]. Acceptance of this document constitutes the agreement by the recipient that no unpublished information contained herein will be published or disclosed without prior written approval.

DoCTR

response to inflammatory cytokines. Clusters of differentiation are used for identification of neutrophils, to determine migration, phagocytosis and activation. Some of the CDs expressed in the neutrophil surface include those related to neutrophil adhesion¹⁹ (CD11b, CD11c, CD16 CD62L, and CD54); Immunoglobulins (CD32) and anaphylatoxins (CD88, CD66b)²⁰. The effects of granulocyte-macrophage colony stimulating factor (GM-CSF), are well described regarding encoding of CDs in response to bacteria and DAMPs²¹; with significant enhancement of the pro-inflammatory activity of PMNs, and is consistent with the concept of a significant biosynthetic capacity for PMN cells.

Neutrophils produce large quantities of reactive oxygen species. Although reactive oxygen species (ROS) are generated by neutrophils to control infection, this activity may also alter local healthy tissue. Hydrogen peroxide and superoxide are generated during phagocytosis of particles or elevated concentration of chemoattractants²². A sign of neutrophil activation is an acute increase in oxygen consumption (respiratory burst) that is mediated by a membrane-bound complex, nicotinamide adenine dinucleotide phosphate (NADPH)-dependent oxidase²³. NADPH mediates formation of superoxide anion after dismutation to hydrogen peroxide, which in turn is involved in promoting formation of secondary reactive products, such as singlet oxygen, hypochlorous acid and hydroxyl radicals. The end point of this process is neutrophil degranulation with subsequent enzyme degradation of host and microbial tissues.

Regulatory PMN cells are important for host protection against injury. PMN cells have demonstrated dual properties in regulating a specific response to sterile and non-sterile injury by using different mechanisms to induce inflammation or anti-inflammation (immunosuppression)²⁴. During infectious injury mediated by gram positive, gram negative bacteria, fungus, PMN may influence activation of T cells which produce interferon γ (IFN- γ), and in turn IFN- γ acts as a potent activator of PMN locally²⁵; or can involve Toll -like Receptors (TLRs) such as TLR-2, TLR-4 and TLR-9²⁶. We are interested in studying the response of PMNs to injury secondary to the ETT, by analyzing several indicators of PMN activation regarding inflammation and anti-inflammation.

Several systemic diseases and certain antibiotics may alter PMN responsiveness to injury. A variety of systemic diseases such as diabetes, rheumatoid arthritis, acute lung injury and several others may affect local PMN responses to injury by altering inflammation, apoptosis and proper anti-inflammation. In the case of diabetes with microangiopathy surface receptor CD11b was elevated and CD62L was decreased²⁷. The impact of macrolide antibiotics and in particular azithromycin in the improved outcome of respiratory diseases such as acute lung injury (ALI), community-acquired pneumonia (CAP) and ventilator associated pneumonia (VAP) appear to be mediated by its anti-inflammatory properties. In particular azithromycin may affect PMN activation, PMN survival, oxidative burst, and attenuation of nuclear factor- κB ²⁸, therefore modulating the inflammatory response. It is not known the exact effect of these systemic factors in the local expression of neutrophils at the tracheal level, therefore our interest to compare local and systemic PMN activation in the healthy subject.

CONFIDENTIAL: This document is the intellectual property of [name]. Acceptance of this document constitutes the agreement by the recipient that no unpublished information contained herein will be published or disclosed without prior written approval.

DoCTR

A variety of biomaterials activate PMN in blood. The endotracheal tubes contain a biomaterial known as di-(2-ethyl-hexyl)-phthalate or DEHP as it is commonly known. Studies in human and rat blood have shown its ability to increased CD-11b expression in PMN cells²⁹. The effects on PMN of neonates also include inhibition of chemotaxis, stimulation of oxidative metabolism, and upregulation of NADPH-oxidase-1³⁰. DEHP is the only plasticizer approved for human devices by the U.S. Food and Drug Administration. Studies of materials involved either human blood samples, or *in vitro*, or rat models, none have *in vivo* local activation of PMN cells.

Significance of intubation related sore-throat in airway inflammation VAT/VAP:

Placement of an endotracheal tube results in tracheal injury. We hypothesize that intubation-related sore throat is associated with neutrophil activation in the airway. To the best of our knowledge the association of neutrophil activation in the subglottic area and intubation-related sore throat has not been studied. We contend this is a relevant clinical phenomenon, which has implications beyond the larynx and pharynx because studies have shown that there is a link between upper (endotracheal intubation) and lower respiratory inflammation or infection (VAP)³⁶. Although not all patients develop sore throat following intubation they do have elevated neutrophils in the subglottic area, suggesting the possibility of the existence of different neutrophils phenotypes regulating inflammation in the trachea. Therefore, to provide better insight into the pathophysiology of upper airway inflammation and progression to VAT and VAP we propose to analyze PMN-mediated inflammation in the trachea through characterizing neutrophil phenotype and function in our patient population.

Neutrophils have a fundamental role in inflammation as effectors cells, capable of responding to sterile tissue injury. Expression of surface receptors on the neutrophils under certain conditions may result in an activated phenotype that will enhance their ability to migrate, produce more reactive oxygen species and delay apoptosis. Unique PMN receptors –cluster of differentiation CD- had been found in blood of patients with respiratory diseases (asthma, COPD) and had been correlated with severity of clinical manifestations. Neutrophil activity has been extensively investigated during systemic inflammation; however, the characterization of neutrophil phenotype and function in local sites of inflammation is less well defined. Placement of an endotracheal tube (ETT) is performed for a variety of medical conditions including short term general anesthesia. We are interested in analyzing the neutrophil phenotype *in vivo* while the ETT is in direct contact with the tracheal tissue in an attempt to correlate them with the occurrence of sore throat. A better understanding of neutrophil trafficking and CD expression in the upper airway may offer new and more precise therapeutic targets to prevent local and distant disease.

The glutathione-S-transferase mu1 (GMSTM1) null genotype is fairly common in the general population (40-43%) and in all ethnicities (Montero R. et al. 2007. *Hum Biol*). The presence of GMSTM1 is associated with increased risk for cancer (Zhong S, et al. 1993. *Carcinogenesis*) and inflammatory diseases of the airway and lungs (Alexis NE, et al. 2009. *J Allergy Clin Immunol*; Wu W, et al. 2012. *Free Radic Biol Med*). Studies have shown that reactive oxygen species (ROS) are abnormally generated in GMSTM1-null phenotype (Yang Y, et al. 2009. *Hypertension*). Since neutrophil activity is closely link to ROS activity and we have demonstrated in our studies of human tracheal lavages that ROS is significantly elevated in those with tracheal injury, we would want to

CONFIDENTIAL: This document is the intellectual property of [name]. Acceptance of this document constitutes the agreement by the recipient that no unpublished information contained herein will be published or disclosed without prior written approval.

DoCTR

analyze the presence of GMSTM1 in all the specimens collected and in the prospective human donors.

